The objective of this study is to compare two different types of lower limb prosthetic systems that remove sweat (one new commercially-available system and one experimental system that uses an experimental liner and suspension with a standard socket and commercially-available foot) with the participant's own "as prescribed" prosthetic system. We aim to determine which one provides people, who are very active or work in demanding environments, with a secure fit despite a significant amount of residual limb sweating and does so without compromising residual limb health and comfort. The two study prosthetic systems that remove sweat are: 1) a new, commercially-available, perforated elastomeric liner intended to transport perspiration away from the skin (Uniprox's SoftSkin Air) and 2) an improved version of the Dynamic Air Exchange (DAE) prosthetic system we developed, the Dynamic Air Exchange - Rising Edge Design (DAE-RED). Anecdotal reports suggest the perforated liner can maintain a secure fit/suspension during periods of significant sweating but may result in excessive skin dryness and discomfort. The DAE-RED expels sweat using a vacuum pump like its predecessor but incorporates a body-weight activated pump to minimize battery consumption and a revised ventilation system that removes the need for undesirable exterior tube connections.

Purpose: The purpose of this study is to compare two different, lower limb prosthetic systems purported to remove sweat and the participant's own "as prescribed" system to identify which is most effective at maintaining limb skin health and a secure fit, when worn in conditions that result in a significant amount sweating. We will also compare how comfortable the three prostheses are when participants do their usual activities while at home, work, and in the community.

We hope this work will result in widespread adoption of the prosthesis that maximizes adherence to the residual limb in demanding environments while maintaining the health and comfort of the limb. Improving prosthetic adherence will expand the conditions under which individuals with lower limb amputation can confidently work despite significant sweating. Improvements in prosthetic limb adherence are especially relevant to younger, more active Veterans and individuals still on active duty, who have an amputation.

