5.7 Data Analysis

Data collected from the laboratory-based experiments will be used to test three hypotheses. The distance that the proximal border of the liner moved from its pre- to post-treadmill walk in the environmental chamber position (marked on the skin) will be compared and enable us to test hypothesis: (H_{1.1}) *The amount of slippage (loss of adherence) will be different between the three prosthetic systems.* The tare weight (wet – dry conditions) of perspiration expelled from Uniprox and DAE-RED prostheses will be compared and enable us to test hypothesis: (H_{1.2}) *The amount of perspiration expelled will be different between the Uniprox and DAE-RED.*

Data collected from the field-based experiments will be used to test three hypotheses. The mean result from the three measures of skin hydration from the posterior compartment of the residual limb will be compared and enable us to test hypothesis (H_{2.1}) *Residual limb skin hydration will be different between the three prosthetic systems.* The mean result from the three measures of transepidermal water loss from the posterior compartment of the residual limb will be compared and enable us to test hypothesis (H_{2.2}) *Residual limb transepidermal water loss will be different between the three prosthetic systems.* The Socket Comfort Score will be used to access the comfort of the three prosthetic systems and enable us to test hypothesis (H_{2.3}) *The Socket Comfort Score will be different between the three prosthetic systems.*

The statistical analysis to test these hypotheses will require six linear mixed effects regression analyses. These analyses will test for differences by prosthetic system (as-prescribed, Uniprox, DAE-RED) with random effects for subject and subject by prosthetic system interaction. The experiment-wise significance will be set a priori at an alpha level of $p<0.05$ and a Bonferroni adjustment will be applied for multiple comparisons. All analyses will be performed using existing software (R Foundation for Statistical Computing with lme4 and multcomp packages, Vienna, Austria). Exact p-values will be reported for each test.

Statistical Power Analysis

We conducted several power analyses to explore the statistical strength of our study design and estimate the number of subjects necessary to obtain meaningful results.

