A second exploratory power analysis for the skin hydration ($H_{2.1}$) metric was performed using published values from Firooz [36]. Using the same instrument (Corneometer CM825; Courage & Khazaka, Köln, GER) proposed in our study, Firooz measured skin hydration of subjects diagnosed with atopic dermatitis ($n=30$) and age-matched controls ($n=30$) at several upper body sites including the dorsal surface of the hand. Atopic dermatitis is a chronic, reoccurring, pruritic form of dermatitis prone to dry skin and other complications. Firooz found skin hydration of 38.9 ± 12.8 and 29.6 ± 10.0 (arbitrary units) for the control group and atopic dermatitis group, respectively. While Firooz's study used a between-subject experimental design, our proposed within-subject study can be expected to have less variance. If we assume a standard deviation of 12.8 for the difference between study prosthetic systems and a difference between means of 9.3, there is an 80% probability to find a significance difference between prosthetic systems with *17 subjects*. Choi [37] also used the same instrument to measure skin hydration, but at eight different anatomical sites including the leg posterior surface, on children with extrinsic atopic dermatitis ($n=41$) and age-matched controls ($n=8$). Choi found skin hydration of 64.8 ± 14.4 and 52.1 ± 14.2 (arbitrary units) for the control group and atopic dermatitis group, respectively. Choi also used a between-subject experimental design which

would likely have greater variance than our proposed within subject experimental design. Assuming a standard deviation of 14.4 for the difference between study prosthetic systems and a difference between means of 12.7, there is an 96% probability to find a significance difference between prosthetic systems with *20 subjects*.

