A third exploratory power analysis for the transepidermal water loss ($H_{2.2}$) metric was performed, also using results reported by Choi [37]. Using the same instrument (Tewameter TM300; Courage & Khazaka, Köln, GER) proposed in our study, Choi measured transepidermal water loss as described above and found the transepidermal water loss of 16.5 ± 8.17 and 28.8 ± 18.8 g/m²/h for the controls and extrinsic atopic dermatitis children, respectively. If we assume a standard deviation of 13.0 for the difference between study prosthetic systems and a difference between means of 12.3, there is an 97% probability to find a significance difference between prosthetic systems with *20 subjects*. We note Choi reported a large difference in variances between groups (8.17 and 18.8 g/m²/h), and the power analysis is particularly sensitive to different variances. We used a value mid-way between the two groups; using a greater variance of 18.8 results in a 79% probability to find a difference with *20 subjects* while using a smaller variance of 8.17 results in a 99% probability to find a difference with *20 subjects*.

These analyses provide confidence that our proposed within-subject experimental design will provide meaningful results with a sample population of 20 subjects.

Supplemental Measures

Absorbent pads placed on the skin of the contralateral limb during the laboratory protocol will be used as a control measure of perspiration. The tar weight of the pad will be used to calculate the perspiration rate by dividing the weight of the pad by its surface area and the donned duration, expressed in grams per meter square of body surface area per hour (g m⁻² h⁻¹). We will perform a linear mixed effects regression analysis on these samples to determine if there were differences in perspiration rate across study prosthetic systems (independent variable). If a significant difference is found, we will perform an analysis of co-variance in consultation with our Center's biostatistician to quantify the effects on the study results.

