Title: Novel Lower-Limb Prostheses: Comparing Adherence, Perspiration, and Residual Limb Skin Health in a Hot, Humid Environment and During Activities of Daily Living

NCT03900845

Document Date: 10Apr2023

Statistical Analysis Plan

Linear mixed effects regression was used to assess the association between outcomes and suspension system. Study participant was modeled as random. Hypothesis testing was carried out using conditional F-tests. Results are summarized as means \pm standard error (SE) for each suspension system and mean differences among groups, \pm SE, 95% confidence intervals and p-values to test if pairwise differences were significant using Tukey's method to adjust for multiple comparisons. Differences from the baseline measurements were not assessed. Variables with heterogeneous variances were analyzed using log transformations with mean differences back transformed into the original units and pairwise differences presented as ratios. Significance was reported with a nominal threshold of $p < 0.05$, supplemented by effect sizes (Hedges' g). Effect sizes were interpreted as small ($0.2 \leq g \leq 0.5$), moderate ($0.5 \leq g \leq 0.8$), and large ($g \geq 0.8$) (Cohen, 2013). Analyses were carried out using R 4.2.1 (Team RC, 2022), and packages tidyverse, lme4, emmeans and kableExtra (Wickham, 2019; Bates, 2015; Lenth, 2022; Zhu, 2023).

Cohen J. Statistical power analysis for the behavioral sciences. New York, NY, Academic Press, 1977.

Team RC. R: A language and environment for statistical computing [Internet]. Vienna, Austria: R Foundation for Statistical Computing; 2022. Available from: www.R-project.org

Zhu H (2023). *kableExtra: Construct Complex Table with 'kable' and Pipe Syntax*. R package version 1.3.4.9000, <https://github.com/haozhu233/kableextra>.

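### The skin hydration and water loss powers are for a single unadjusted paired test; for the adjusted pairwise comparisons, the stated 80% at 17 subjects is 63–70%

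*Protocol*

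**What the plan says.** Protocol section 5.7 plans mixed-model comparisons of three systems (as-prescribed, Uniprox, DAE-RED). On error control it says "The experiment-wise significance will be set a priori at an alpha level of" 0.05 and that "a Bonferroni adjustment will be applied for multiple comparisons". It does not say which comparisons form the family.

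The power subsection of 5.7 gives five figures for H2.1 and H2.2. Each rests on one mean difference and one standard deviation (SD) of the difference. No alpha is stated with them.

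- Hydration, first published source: difference 9.3, SD 12.8; "there is an 80% probability to find a significance difference between prosthetic systems with" 17 subjects.
- Hydration, second published source: difference 12.7, SD 14.4; 96% with 20 subjects.
- Transepidermal water loss (TEWL): difference 12.3, SD 13.0; 97% with 20 subjects.
- TEWL with the larger group SD: "using a greater variance of 18.8 results in a 79% probability to find a difference with" 20 subjects.
- TEWL with the smaller group SD, 8.17: 99% with 20 subjects.

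The subsection concludes that the within-subject design "will provide meaningful results with a sample population of 20 subjects".

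The SAP states "Hypothesis testing was carried out using conditional F-tests", and that pairwise differences are tested "using Tukey's method to adjust for multiple comparisons".

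**The concern.** The power figures look as if they belong to a single comparison of two systems, whereas each outcome has three pairwise comparisons and both documents adjust for that. If so, the stated power is too high for the tests from which pairwise conclusions will be drawn.

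Those conclusions are the point of the study. The Protocol's purpose statement is to "identify which is most effective at maintaining limb skin health and a secure fit". A significant overall F-test across three systems does not show which one differs; that takes the adjusted contrasts. A reader weighing a non-significant adjusted contrast against the stated 80% or 79% would put too much weight on it as evidence of no difference.

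**Working it through.** **Inputs.** The differences, SDs, subject numbers and stated powers are those of the power subsection of section 5.7. The text calls 18.8 and 8.17 variances, but they are the reported group SDs and are used as SDs. Two-sided testing is assumed because the hypotheses are non-directional. The plan's SD is taken as the SD of every pairwise difference, with equal variances for the pooled tests. The family is assumed to be the three pairwise contrasts within one outcome.

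**Formula.** With noncentrality δ = (difference / SD) × √n, power = P(|T| > c), where T is noncentral t with noncentrality δ. Only the critical value c and the degrees of freedom (df) change:

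- unadjusted paired test: c = t(0.975; n−1)
- Bonferroni over three, paired df: c = t(1 − 0.05/6; n−1)
- Bonferroni over three, pooled df: c = t(1 − 0.05/6; 2(n−1))
- Tukey, three means, pooled df: c = q(0.95; 3, 2(n−1)) / √2

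**Step 1: reproduce the stated 80%.** δ = (9.3/12.8) × √17 = 0.7266 × 4.123 = 2.996. With df 16 and c = 2.120, power is 80.3%. Other readings of the 80% do not fit: one-sided gives 88.9%, a normal approximation 85.0%, and two independent groups of 17 give 56.3%.

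**Step 2: the same scenario, adjusted, n = 17.**

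- Bonferroni, paired df 16: c = 2.673, power 63.0%
- Bonferroni, pooled df 32: c = 2.526, power 68.0%
- Tukey, pooled df 32: c = 2.457, power 70.3%

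**Step 3: all scenarios.** At n = 20 the critical values are 2.093 (unadjusted), 2.625 (Bonferroni, paired), 2.505 (Bonferroni, pooled) and 2.439 (Tukey, pooled).

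| Difference / SD | n | δ | Stated | Unadjusted | Bonferroni, paired df | Bonferroni, pooled df | Tukey, pooled df |
|---|---|---|---|---|---|---|---|
| Hydration 9.3/12.8 | 17 | 2.996 | 80% | 80.3% | 63.0% | 68.0% | 70.3% |
| Hydration 9.3/12.8 | 20 | 3.249 | – | 86.9% | 72.8% | 76.8% | 78.7% |
| Hydration 12.7/14.4 | 20 | 3.944 | 96% | 96.2% | 89.4% | 91.9% | 92.9% |
| TEWL 12.3/13.0 | 20 | 4.231 | 97% | 98.0% | 93.4% | 95.3% | 95.9% |
| TEWL 12.3/18.8 | 20 | 2.926 | 79% | 79.3% | 62.2% | 66.3% | 68.6% |
| TEWL 12.3/8.17 | 20 | 6.733 | 99% | >99.9% | >99% | >99% | >99% |

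For the base TEWL case the exact midpoint SD, (8.17 + 18.8)/2 = 13.485, gives 97.2% unadjusted, which matches the stated 97%.

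**Step 4: subjects needed for 80% at 9.3/12.8.**

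- Unadjusted: 17 (80.3%)
- Tukey, pooled df: 21 (81.0%; 20 gives 78.7%)
- Bonferroni, pooled df: 22 (81.5%; 21 gives 79.3%)
- Bonferroni, paired df: 23 (80.5%; 22 gives 78.2%)

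**Step 5: the overall F-test for comparison.** It has df 2 and 2(n−1), and λ = n × Σ(mean − grand mean)² / (SD²/2). The sum is difference²/2 if the third mean lies midway and 2 × difference²/3 if it equals one of the other two.

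- 9.3/12.8, n = 17: λ = 8.97 to 11.97, power 73% to 85%
- 9.3/12.8, n = 20: λ = 10.56 to 14.08, power 80% to 91%
- 12.3/18.8, n = 20: λ = 8.56 to 11.42, power 71% to 84%

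**Step 6: the enrolment ceiling.** At n = 40 with Bonferroni over three and paired df, power is 97.9% (9.3/12.8), 99.9% (12.7/14.4), above 99.9% (SD 13.0) and 94.4% (SD 18.8). The SD 8.17 scenario already exceeds 99% at n = 20.

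**The case against.** The strongest reply is that H2.1 and H2.2 only say the three systems will differ, and the SAP assigns hypothesis testing to F-tests, which the pairwise adjustment leaves alone. F-test power at 17 subjects, 73–85%, brackets the stated 80%. This stands as far as it goes, and it is why the F-test figures should appear beside the pairwise ones. But the stated figures are not F-test figures: they use one mean difference and one SD of the difference, give no third mean, and match a paired test.

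Second, the 63% end and the 23 subjects use paired df, whereas both documents plan mixed models. With pooled df throughout, the range is 68–70% at 17 subjects and 77–79% at 20, and Bonferroni needs 22. This is fair; it narrows the gap but does not close it.

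Third, at 20 subjects Tukey's 78.7% is about one point short of 80%, and the Protocol expects a within-subject SD below its between-subject sources. An SD of 12.6 instead of 12.8 would give 80.1%. True, but the Protocol gives no smaller SD and computes with 12.8.

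Fourth, SD 18.8 is the Protocol's own pessimistic case, already shown at 79% with a warning about sensitivity to variance. That disclosure is itself on the unadjusted basis.

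Finally, the analyses are labelled exploratory and up to 40 may enrol. The label carries little weight, since the section rests its sample-size conclusion on them. The ceiling does limit the consequence, but it is not a target and nothing ties it to the power calculation.

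**Conclusion.** The concern holds. The Protocol's sums are right for the test they used, but that is not the adjusted pairwise test from which the plan will draw its conclusions. On the plan's own inputs, the stated 80% at 17 subjects is 63–70%. At 20 subjects, two of the five scenarios fall below 80% and the other three stay at 89% or more.

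This rests on a family of three contrasts within one outcome and on the plan's SD applying to every pairwise difference. A family spanning several outcomes, which the Protocol's experiment-wise wording could mean, would lower power further: at 17 subjects with paired df, 51% if alpha is divided by six and 37% if by fifteen.

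What fails is the stated justification, not the feasibility of the study. The slippage figure (99% with 10 subjects) is outside this conclusion, because the Protocol does not give the SD of the difference needed to recompute it.

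**What to change.** 1. Choose between the Protocol's Bonferroni and the SAP's Tukey adjustment, and state in one sentence which comparisons form the family.
2. Restate the five H2.1 and H2.2 powers for the adjusted pairwise test, with the alpha and df used. Label each figure as pairwise or overall F-test; for an F-test figure, state the assumed third mean.
3. In the 9.3/12.8 scenario, replace 17 subjects for 80% power with 21 (Tukey, pooled df) or 23 (Bonferroni over three, paired df; 22 if df are pooled).
4. Leave enrolment as it is.

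The cost is a short recalculation and a few sentences. The only downside is that the stated powers become less favourable.

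### The power calculation for transepidermal water loss uses independent-group SDs as the SD of the within-subject difference and states no correlation, so its 97% and 99% are not supported by its inputs

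*Protocol*

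**What the plan says.** The Statistical Power Analysis part of Protocol section 5.7 takes its TEWL inputs from a published comparison of two separate groups, reported as "transepidermal water loss of 16.5 ± 8.17 and 28.8 ± 18.8 g/m²/h for the controls and extrinsic atopic dermatitis children". The gap between the group means becomes the effect, and the assumption is put this way: "If we assume a standard deviation of 13.0 for the difference between study prosthetic systems and a difference between means of 12.3". The choice of 13.0 is explained as follows: "We used a value mid-way between the two groups". With 20 subjects the stated power is 97%.

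Two sensitivity values follow. The larger group SD, 18.8, gives a stated 79%. The other is described thus: "while using a smaller variance of 8.17 results in a 99% probability to find a difference". Both are called variances, although they are the SDs quoted a few lines earlier.

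The skin hydration analysis in the same section is built the same way. For its first source the protocol says that "our proposed within-subject study can be expected to have less variance", and continues: "If we assume a standard deviation of 12.8 for the difference between study prosthetic systems". The 12.8 is the larger of that source's two group SDs. For the second source it enters 14.4, again the larger group SD. The section concludes that 20 subjects will give meaningful results. Neither the protocol nor the SAP states a within-subject correlation.

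**The concern.** Each participant wears every system, so the comparison is of paired differences. Their SD depends on the SD under each system and on the correlation between a participant's measurements under the two systems. A group SD from a study of unrelated people is a different quantity. It may be larger or smaller than the SD of the difference, depending on the correlation.

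The protocol treats the paired design as automatically reducing variance. That holds only when the correlation is high enough. Without a stated correlation, a reader cannot tell whether 97% is cautious or optimistic, or what the 79% and 99% cases represent. These figures are part of the stated basis for 20 subjects.

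**Working it through.** **Inputs (Protocol 5.7).** TEWL: SDs 8.17 and 18.8, difference 28.8 − 16.5 = 12.3, n = 20. Hydration, first source: SDs 12.8 and 10.0, difference 9.3, n = 17. Hydration, second source: SDs 14.4 and 14.2, difference 12.7, n = 20. Alpha is 0.05. Two-sided testing is my assumption, and it reproduces the stated 79%.

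**Step 1: reproduce the stated TEWL figures.** Paired t-test power from the noncentral t distribution, df = 19, noncentrality = (12.3 / SD of difference) × √20:

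| SD entered | Noncentrality | Power | Stated |
|---|---|---|---|
| 13.0 | 4.23 | 98.0% | 97% |
| 13.485 | 4.08 | 97.2% | – |
| 18.8 | 2.93 | 79.3% | 79% |
| 8.17 | 6.73 | >99.9% | 99% |

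So the entered values were used as SDs of paired differences. The true midpoint is (8.17 + 18.8)/2 = 13.485. The stated 97% fits that value slightly better than 13.0.

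**Step 2: what the entered SDs imply if the two systems carry the two group SDs.** SD_diff² = s1² + s2² − 2·rho·s1·s2, with s1² + s2² = 66.75 + 353.44 = 420.19 and 2·s1·s2 = 307.19. The minimum, at rho = 1, is 18.8 − 8.17 = 10.63. Solving for rho:

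- 8.17: (420.19 − 66.75)/307.19 = 1.15, infeasible
- 13.0: (420.19 − 169.00)/307.19 = 0.82
- 13.485: (420.19 − 181.85)/307.19 = 0.78
- 18.8: (420.19 − 353.44)/307.19 = 0.22

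**Step 3: the other reading, one common SD.** If both systems share an SD s and s is also entered as the SD of the difference, then s² = 2s²(1 − rho), so rho = 0.5 in every scenario.

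**Step 4: TEWL power from both group SDs, n = 20, two-sided 0.05.** The rho values are assumptions.

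| rho | SD of difference | Power |
|---|---|---|
| 0 | 20.50 | 72% |
| 0.3 | 18.11 | 82% |
| 0.5 | 16.33 | 89% |
| 0.7 | 14.32 | 95% |

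At rho = 0, 24 subjects give 80% and 40 give 96%.

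**Step 5: hydration, same method.** The SD of the difference falls to the entered group SD only when rho reaches 10.0/(2 × 12.8) = 0.39 for the first source and 14.2/(2 × 14.4) = 0.49 for the second.

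| Case | rho 0 | rho 0.3 | rho 0.5 | Stated |
|---|---|---|---|---|
| First source, n = 17 | 60% | 75% | 87% | 80% |
| First source, n = 20 | 68% | 82% | 92% | – |
| Second source, n = 20 | 76% | 89% | 96% | 96% |

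**The case against.** The best defence is that the protocol openly assumes an SD for the difference and uses the published SDs only to set its scale. It never says that one prosthesis would have the SD of healthy children and another that of children with dermatitis. This stands. A reader might infer that the 8.17 case is impossible outright, or that 97% always requires a correlation near 0.8. Both hold only under the unequal-SD reading. That reading is natural, because the 12.3 effect comes from the same two groups and the protocol itself stresses their unequal spread, but the text does not fix it. The common-SD reading still needs an unstated correlation of 0.5.

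A reader might also infer a calculation error. There is none: the powers reproduce within about one percentage point for the SDs entered.

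Nor does the disclosed 79% to 99% range miss the plausible values altogether. Correlations of 0.3 to 0.7 give 82% to 95%, which lies inside it. The low end is too favourable only if the correlation is below about 0.22. The protocol also labels these analyses exploratory and warns that they are sensitive to the variances. The second hydration source returns its stated 96% at a correlation of 0.5.

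Finally, the SAP is dated April 2023 and written in the past tense, so a correction now alters planning text and no estimate or test. That limits the consequence but does not make the stated basis for 97% and 99% sound.

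**Conclusion.** The point holds as a fault in the SD input. The TEWL figures of 97% and 99% rest on independent-group SDs used as the SD of a paired difference, with no correlation given. Using both group SDs, power with 20 subjects runs from about 72% to 95% over assumed correlations of 0 to 0.7. The documents support no particular value in that range. The 8.17 scenario is infeasible if the systems have unequal SDs of 8.17 and 18.8, and otherwise needs an unstated 0.5. The mismatch between 13.0 and the midpoint is real but moves power by less than one point.

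A reader might infer that the study is too small. The documents do not support that on this ground. Even at zero correlation, 24 subjects give 80% unadjusted power, and enrolment is allowed up to 40. The recomputed powers, like the protocol's own, leave out the planned multiplicity adjustment (Bonferroni in the protocol, Tukey in the SAP). Adjusted power would be lower, but the protocol gives no Bonferroni divisor, and multiplicity is a separate matter from the SD input.

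**What to change.** In the Statistical Power Analysis part of Protocol section 5.7:

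- State the assumed within-subject correlation and its basis, and compute the SD of the difference from both group SDs.
- Remove the 8.17 scenario with its 99%, or justify it.
- Replace the 97% for TEWL at 20 subjects with about 72%, 82%, 89% and 95% at correlations of 0, 0.3, 0.5 and 0.7, labelled as assumptions.
- Restate hydration at 20 subjects for correlations of 0, 0.3 and 0.5: 68%, 82% and 92% for the first source, and 76%, 89% and 96% for the second. Beside the first source's 80% at 17 subjects, give 60%, 75% and 87%.
- Reconcile 13.0 with its description as mid-way, and call 8.17 and 18.8 SDs.
- Say that these powers exclude the planned multiplicity adjustment.

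The cost is wording only. The stated power becomes less favourable over most of the range, and the sample size stays as planned.
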